Study Title

Motor Imagery: A Pilot Intervention for Improving Gait and Cognition in the Elderly

Objectives:

Primary. Compared to a visual imagery intervention group, participants who are enrolled in the motor imagery intervention (MI) group will demonstrate:

P1: Significant improvements in gait speed during actual Walking and Walking While Talking

Secondary. Compared to a visual imagery intervention group, participants who are enrolled in the motor imagery intervention (MI) group will show:

P 2.1: Significant improvements in cognitive performance during Talking and Walking While Talking

P 2.2: Change in blood-oxygen-level dependent signal during Walking and Walking While Talking

Design and Outcomes

The investigators propose to conduct a single-blind randomized clinical trial to test the efficacy of a phone-based motor imagery intervention for improving gait and cognition in older adults between 65 and 85 years old

[figure not shown]

Figure 1. Participant Flow

Interventions and Duration

Participants will be randomized into either a 12-week phone-based motor imagery intervention or visual imagery intervention (active control condition). Both groups will complete 36 (15-minute) sessions (9 hours).

Participants will receive gait, mobility, cognitive and neuroimaging assessments at baseline and post-intervention (14-18 weeks after intervention). Baseline and post-intervention assessments will last about 3 hours over 1 day.

Sample Size and Population

We will enroll 48 cognitively-healthy older adults (24 in each group).

STUDY TEAM ROSTER

Principal Investigator:

[name]
Einstein College of Medicine,
[name]
[contact]
[contact]

[contact]

Main responsibilities/Key roles: She will coordinate efforts between team members, supervise implementation of study measures and supervise data collection. She will develop data analysis plans as well as scientific presentations and manuscripts based on the research findings.

Mentor:

[name]
Albert Einstein College of Medicine,
[name]
[contact]
[contact]

[contact]

Main responsibilities/Key roles: He will be responsible for the oversight of [name] responsibilities and for establishing benchmarks to ensure successful completion of this intervention. He will also be involved in developing data analysis plans as well as scientific presentations and manuscripts based on the research findings.

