The first aim of this research is to establish the efficacy of this imagined gait protocol to improve gait and EF in the elderly. We propose a pilot Randomized Clinical Trial (RCT) of 48 cognitively-healthy elderly adults who will be randomly assigned to an imagined gait intervention or an Active Control (AC; non-mobility related visual imagery) condition. The imagined gait (or AC) protocol will be administered during each study visit, and over the phone three times a week for three months (15 min/session, total of 36 sessions). Each participant will complete two study visits (pre and post). Pre-post intervention changes in gait velocity (cm/s) and cognitive performance (percent of correct letters provided; (correct/error x correct) x 100) during actual W, T and WWT will be our primary outcome measures. Age, Sex and Education will be covariates in all analyses. Other variables/covariates will be recorded (e.g. medical illnesses and history of falls), and carefully examined for potential inclusion as covariates in upcoming full-scale RCT.

The second aim is to determine neuroplasticity changes in response to our imagined gait intervention. To this end, participants will complete the imagined gait protocol (iW, iT and iWWT) during fMRI scanning at the pre and post-intervention study visits. We predict that our imagined gait protocol engages neural systems linked to actual gait and EF, while the AC condition engages neural systems linked to visual processing and imagery in general. We further predict that the neural systems engaged during our imagined gait protocol are strengthened following our imagined gait intervention.

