3 STUDY DESIGN

Design: We propose a single-blind study of cognitively-healthy older adults randomized to a phone-based motor imagery or visual imagery (active control) intervention for 12 weeks (36 sessions)

Outcomes: The primary outcome is post-intervention change in gait speed during actual walking and walking while talking.

Secondary and tertiary outcomes include improvements in cognitive performance during Talking and Walking While Talking, changes in blood-oxygen-level dependent signal during Walking and Walking While Talking, improvement in executive function, and other mobility-related cognitive processes (speed of processing, memory and spatial navigation), and improved gait variability and other quantitative gait parameters during walking and walking while talking (see Clinicaltrials.gov-NCT02762604 for a comprehensive list).

Study population: 48 Bronx and Westchester county residents between 65 and 85 years old will be randomized into a phone-based motor imagery or visual imagery (control) intervention for 12 weeks (36 sessions)

Study location: Pre and post-intervention visits will be held at the Albert Einstein College of Medicine.

Approximate duration of enrollment period and follow-up: Potential recruits who meet eligibility criteria on the telephone are invited to baseline assessment and then randomized to motor imagery or visual imagery intervention. Baseline study assessments are limited to 180 minutes over 1 day to avoid fatigue. Telephone assessments are 15 minutes. Post-intervention assessments will be conducted within 4 weeks of the completion of the intervention.

We plan to enroll and randomize 48 participants over 36 months (1-2 per month). If necessary, we will ask for a no cost extension to allow for additional time to process and analyze the data, write manuscripts, and possibly apply for a follow-up grant.

Randomization and Blinding: We will include a number of methods to reduce bias.

- Selection bias will be reduced by concealing treatment allocation until the participant is entered into trial.
- Primary outcome is an objective endpoint (gait speed) and not subjective mobility complaints.
- Motor imagery and visual imagery interventions will be administered individually, and at non-overlapping times.
- Participants and study staff will be instructed not to disclose group assignment or details of interventions.

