5.4 Adherence Assessment

Sustaining adherence represents a major challenge in any RCT involving older adults. The phone-based delivery of the RCT improves likelihood of adherence. We have also incorporated multiple methods to promote adherence and reduce possibility of missing data.

- A permanent staff contact will be provided for each participant in the motor imagery and visual imagery intervention groups.
- Transportation and snacks will be provided on pre and post intervention assessment days.
- All participants will be compensated for attending in-house or telephone sessions (\$50 for the baseline visit, \$25 for the phone-based intervention, and \$50 for the post-intervention visit, for a total of \$125 for the study).

We propose to over-enroll by 20% to account for any attrition. Methods to account for non-compliance and missing data:

- Protocol violations. Subjects who miss 6 sessions due to any reason will be excluded from main analyses. We will explore dose response by adjusting number of sessions attended as a

covariate.

- We will identify 2 contact persons who do not live with the participant for when participant cannot be reached.
- Flexible scheduling with makeup sessions on alternate days.
- For each in-house study visit, we will allow a four-week window for completion.
- If the participant is acutely ill, is in the hospital, or has a temporary condition that interferes with walking (e.g. ankle sprain), we will attempt to complete the assessment at another time.
- Outcome adjudication. The research team will adjudicate events such as mobility disability in subjects who drop out based on medical interviews, contact interviews, and home assessments as required.

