6 STUDY PROCEDURES

6.1 Schedule of Evaluations

Measures	Test/Type	Visit	Pre-Intervention	During Intervention	Post-Intervention
			Baseline week 0	weeks 1-12	Post week 12-16
Verbal consent	Consent	Phone ✓			
Demographic/Health Screen	Screen	Phone ✓			
Memory Impairment Screen	Screen	Phone ✓			
AD-8 Dementia Screening Interview	Screen	Phone ✓			
Handedness	Screen	Phone ✓			
MRI safety (verbal)	Screen	Phone ✓			
Informed Consent	Consent	Study Visit	✓		
MRI safety (paper)	Screen	Study Visit	✓		✓
Baseline Medical history	Survey	Study Visit	✓		
Sensory Screen	Physical	Study Visit	✓		
Medications	Survey	Study Visit	✓		
Height/Weight/BMI	Physical	Study Visit	✓		✓
Blood Pressure	Physical	Study Visit	✓		✓
SPPB	Physical/Gait	Study Visit	✓		✓
Maze	Cognitive/Gait	Study Visit	✓		✓
Berg Balance Scale	Physical/Gait	Study Visit	✓		✓
Unipedal Stance	Physical/Gait	Study Visit	✓		✓
Stair climbing	Physical/Gait	Study Visit	✓		✓
Grip Strength	Physical/Gait	Study Visit	✓		✓
WRAT & WTAR	Cognitive	Study Visit	✓		✓
RBANS figure copy & delay	Cognitive	Study Visit	✓		✓
Free Cued Serial Recall Test	Cognitive	Study Visit	✓		✓
Falls Questions	Survey	Study Visit/Phone	✓	✓	✓
Falls Efficacy Scale	Survey	Study Visit	✓		✓
Duke Activity Status Index	Survey	Study Visit	✓		✓
Trails A & B	Cognitive	Study Visit	✓		✓
Control Oral Word Association Test	Cognitive	Study Visit	✓		✓

Semantic Fluency	Cognitive	Study Visit	✓	✓
General Mobility Questionnaire	Survey	Study Visit	✓	✓
Geriatric Depression Scale (GDS-30)	Survey	Study Visit	✓	✓
Instrumental ADL Questionnaire	Survey	Study Visit	✓	✓
Flanker Interference	Cognitive	Study Visit	✓	✓
WAIS Digit Symbol Substitution Test	Cognitive	Study Visit	✓	✓
Stroop Interference	Cognitive	Study Visit	✓	✓
Activity Balance Confidence Scale	Survey	Study Visit	✓	✓
SF-12	Survey	Study Visit	✓	✓
CHAMPS	Survey	Study Visit/Phone	✓	✓
Letter Number Sequencing	Cognitive	Study Visit	✓	✓
Social Network Index	Survey	Study Visit	✓	✓
Beck Anxiety Inventory	Survey	Study Visit	✓	✓
MOS Social Support Survey	Survey	Study Visit	✓	✓
Gait Rite	Physical/Gait	Study Visit	✓	✓
Imagery Protocol		Study Visit	✓	✓

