6.2.2 Enrollment, Baseline, and Randomization

Enrollment

The enrollment date is defined as the date that the participants are randomized into either the motor imagery or visual imagery intervention, after they have met all screening criteria and agreed to participate.

Baseline Assessments

For participants who have successfully been screened for eligibility, baseline assessments are performed during their first study session.

Randomization

Randomization will be determined after completion of the baseline assessments. Initiation of the study intervention will take place in the week following the baseline assessment visit.

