6.2.3 Follow-up Visits

Post intervention follow-up assessments will occur within 4 weeks of the completion of the intervention. In addition adverse events will be evaluated over the phone throughout the intervention and at the post-intervention visits. A 4-week window will be allowed for each of the post-intervention assessments.

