6.2.4 Completion/Final Evaluation

Assessments to be completed at the final visit (12 months post-intervention) are listed in Table 5.1.

Losses to follow-up can be classified into non-informative (missing at random (MAR)) and informative censoring (drop out depends on the unobserved outcomes). No adjustment is necessary for non-informative censoring. However, for informative censoring, parameter estimates and resulting tests on hypotheses will be biased without further adjustment. The best way to handle missing data is to avoid it. However, we recognize that despite all our efforts there will be missing data.

Dropouts: We will follow-up with participants who dropped out of the study to determine both their mobility status and reasons for withdrawal. The research team will adjudicate events such as mobility disability in subjects who drop out based on medical interviews, contact interviews, and home assessments as required. Utilization of the telephone based

questionnaire to account for possible non-random drop-out will be administered. If the participant is acutely ill, is in the hospital, or has a temporary condition that interferes with walking (e.g. ankle sprain), we will attempt to complete the assessment at another time.

We also propose intention to treat (ITT) analysis, which includes all randomized participants in the groups assigned, regardless of their adherence with the entry criteria, whether motor imagery was received, and subsequent withdrawal or deviation from the protocol. ITT analysis is pragmatic because it admits noncompliance and protocol deviations, and gives an unbiased estimate of the intervention effect. Handling missing data is a major issue in ITT, and is dealt with by imputation or sensitivity analysis. Our statistician, [name], is very experienced in these methods.

A rich set of telephone-based information will be collected even for those subjects who may drop out. We will utilize this auxiliary information to assess the MAR assumption and combine it into the main model through joint modeling and multiple imputation approaches. [name] has applied these approaches to eliminate or reduce bias in presence of informative censoring in our other aging studies.

7 **SAFETY ASSESSMENTS**

7.1 **Specification of Safety Parameters**

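### The post-test is dated three incompatible ways, and the 3-month residence criterion runs out before most of the window that the schedule uses

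*Combined protocol and SAP*

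**What the plan says.** **Timing of the post-test**
- Precis, Interventions and Duration: assessments "at baseline and post-intervention (14-18 weeks after intervention".
- Section 3: "Post-intervention assessments will be conducted within 4 weeks of the completion of the intervention".
- Section 6.1, schedule column, with baseline as week 0: "Post week 12-16".
- Section 6.2.3: "Post intervention follow-up assessments will occur within 4 weeks of the completion of the intervention".
- Section 6.2.4: "Assessments to be completed at the final visit (12 months post-intervention) are listed in Table 5.1".
- Section 6.2.2, on when training begins: "Initiation of the study intervention will take place in the week following the baseline assessment visit".

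**Number of visits**
- Section 2.1 (Study Rationale): "Each participant will complete two study visits (pre and post".
- Section 5.4 pays $50 for baseline, $25 for the phone sessions and $50 "for the post-intervention visit, for a total of" $125. That is one post-intervention visit.

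**Residence.** Sections 4.1 and 6.2.1 ask that the person intends to stay local for a further 3 months. Section 6.2.1 has the phone-screening answers gone over again at the first visit. Section 3 places both assessment visits at the college.

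**Letter task.** Section 2.1 (Study Rationale) treats cognitive performance as primary alongside gait and scores it as a percentage. Section 1.2 lists it as secondary, for Talking and for Walking While Talking (WWT). Section 9.1.2 takes the count of correct letters, in WWT only, as the main cognitive outcome. The four tests named in Section 9.4.2 do not include the letter task.

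**The concern.** The primary outcome is change in gait speed from baseline to the post-test, so the date of the post-test is part of what is being estimated. An effect within 4 weeks of training is an immediate effect. An effect 14-18 weeks or 12 months later is a retention effect. A reader of the Precis, or of Section 6.2.4, would describe a different trial from the one in the schedule.

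The termination rule in Sections 8 and 9.3 counts 75% retention to the conclusion of the protocol. That date is not defined while a 12-month final visit stands in the text.

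The residence criterion appears to have been set to the length of training and not to the visit that yields the outcome. Someone who plans to leave once training ends meets it, yet may provide no post-test gait speed.

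For the letter task, a count and a percentage can move in opposite directions. Choosing between them after seeing data would leave room for selection.

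**Working it through.** This is calendar arithmetic on one axis, with baseline as week 0.

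**1. The plan's own window.** 36 sessions / 3 per week = 12 weeks. The end of training plus 0 to 4 weeks gives weeks 12-16, which reproduces Section 6.1 and agrees with Sections 3 and 6.2.3. If training starts a full week after baseline (Section 6.2.2), the window becomes 13-17.

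**2. The Precis.**
- Literal reading, after the end of training: 12 + 14 to 12 + 18 = weeks 26-30 (27-31 with the one-week lag). There is no overlap.
- Lenient reading, counted from baseline: weeks 14-18. The overlap with 12-16 is 16 - 14 = 2 of 4 weeks, and with 13-17 it is 17 - 14 = 3 of 4 weeks.

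**3. Section 6.2.4.** 12 + 52 = week 64, or 13 + 52 = week 65. There is no overlap. The schedule has no such column, and the text has no table numbered 5.1; the schedule of evaluations is in Section 6.1.

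**4. Residence.** 3 months = 3 x 365.25/12 = 91.3 days. The clock is assumed to start at baseline, which is the reading most favourable to the plan because Section 6.2.1 reviews screening answers then. The post-test window is 28 days.

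| End of training taken as | Day | Window days inside 3 months | Share beyond |
|---|---|---|---|
| 12 full weeks, start on day 0 | 84 | 91.3 - 84 = 7.3 | (28 - 7.3)/28 = 74% |
| 12 full weeks, start on day 7 | 91 | 91.3 - 91 = 0.3 | (28 - 0.3)/28 = 99% |
| 36th session, earliest | 82 | 91.3 - 82 = 9.3 | (28 - 9.3)/28 = 67% |
| 36th session, latest | 89 | 91.3 - 89 = 2.3 | (28 - 2.3)/28 = 92% |

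For the last two rows, Monday-Wednesday-Friday calls (Section 5.1) put the 36th session 81 or 82 days after the first. A first call on day 1 to day 7 gives 1 + 81 = 82 to 7 + 82 = 89. If the clock starts at the earlier phone screen, coverage is smaller still: with 12 full weeks of training, no start lag and a one-week gap from screen to baseline, about 1% of the window is covered.

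**5. Residence needed to reach the end of the window.** 13 + 4 = 17 weeks = 119 days, and 119/(365.25/12) = 3.9 months.

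**6. Letter score (invented illustration, not trial data).** Moving from 20 correct with 2 errors to 15 correct with none changes the count by (15 - 20)/20 = -25%. The percentage goes from 20/22 = 90.9 to 15/15 = 100.

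**The case against.** The operative sections agree with one another, and the two-visit statement and the payments support them. Staff who follow the schedule would test at about the right time, so the Precis and Section 6.2.4 can be seen as two stray sentences. That is fair as to how easily they are corrected, but it does not make them consistent with the plan.

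Section 9.1.1 links the interval between gait tests to practice effects, which might be thought to raise the stakes. It adds little. The reported gain was under 2% at 8 weeks, every interval considered here is at least 12 weeks, and both arms share the same interval, so a common practice effect largely cancels in the comparison.

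The residence criterion concerns plans and does not bar a later visit. The visit can fall in the first days after training, participants are local, transport is provided, and over-enrolment of 20% is planned. All of this stands. The percentages are shares of calendar days and not of people, and the loss may be small.

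A 17-week requirement might seem to exceed the printed weeks 12-16. With baseline as week 0, a week labelled 16 can run to day 118, so the two are compatible. Section 6.2.3 also has a second sentence allowing a 4-week window for each post-intervention assessment. If that is added to the first 4 weeks, the window becomes 12-20, or 13-21 with the lag. That would contain weeks 14-18 but would still not be the Precis window, and it would contradict Section 6.1.

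The letter score is a separate and lesser matter. Its formula in Section 2.1 is probably a misprint or a text-reading slip and carries no weight here. The omission from Section 9.4.2 can also be debated, since the four tests named there may list only the additional executive measures. The conflicts over rank, score and task do not depend on either point.

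**Conclusion.** The concern holds. The post-test is at weeks 12-16 (or 13-17) in three sections. The Precis puts it at weeks 26-30 literally or 14-18 on a lenient reading, and Section 6.2.4 places a final visit at about week 64-65. No reading makes the three agree.

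The residence criterion is a mismatch and not a contradiction. Under the readings most favourable to the plan, it leaves 67-99% of the on-site window's days uncovered. This assumes that the clock starts at baseline and that 3 months means 91.3 days. How many participants it would cost cannot be derived from the documents.

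The letter-task conflict is real but secondary. These points should be corrected; none of them calls for a change of design.

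**What to change.** - **Precis and Section 6.2.4:** state one post-test within 4 weeks of completing the intervention, as in Sections 3, 6.1 and 6.2.3. Replace the reference to Table 5.1 with the Section 6.1 schedule. Check Figure 1 (not visible in the text reviewed) and the manual of procedures for the same timing.
- **Section 6.2.3:** say whether the 4-week allowance is the same 4 weeks or additional to them.
- **Sections 4.1 and 6.2.1:** require planned residence to the end of the post-test window, at least 17 weeks from baseline, and reconfirm it at the first visit. If the allowance in Section 6.2.3 is additional, the figure becomes 13 + 4 + 4 = 21 weeks.
- **Letter task:** in Section 2.1 (Study Rationale), list cognition as secondary, and check the formula against the PDF and correct it. The sponsor should choose one main score covering both Talking and WWT before data are seen, and name it in Sections 2.1, 9.1.2 and 9.4.2.

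The cost is wording in a handful of places and one eligibility line stated twice. No visit, test or contact is added, because screening answers are already reviewed at the first visit. The downside is that a few people who plan to leave at about 3 to 4 months become ineligible.

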1 STUDY OBJECTIVES

1.1 Primary Objective

Compared to a visual imagery intervention group, the participants who are enrolled in the motor imagery intervention group will demonstrate significant improvements in gait speed (cm/s) during actual Walking and Walking While Talking using an instrumented walkway (GAITRite® electronic walkway system).

1.2 Secondary & Tertiary Objectives

Compared to a visual imagery intervention group, the participants who are enrolled in the motor imagery intervention group will show:

- Significant improvements in cognitive performance during Talking and Walking While Talking
- Changes in blood-oxygen-level dependent signal during Walking and Walking While Talking
- Improvement in executive function, and other mobility-related cognitive processes, such as speed of processing, memory and spatial navigation.
- Improved gait variability and other quantitative gait parameters during walking and walking while talking.

2 BACKGROUND AND RATIONALE

2.1 Background

Age-related gait decline is common among the elderly; with over a third of community-residing elders having clinically diagnosable gait abnormalities. Gait impairment in the elderly is associated with an increased risk of falls, morbidity, hospitalization, mortality, cognitive decline, and dementia (1-5). Physical exercise programs can be used to improve gait in the elderly, but long-term adherence to physical exercise programs is low, and particularly difficult to implement in the elderly (6-8). Determining the efficacy of motor imagery for improving gait and cognition may provide scientific support for a future large-scale randomized controlled trial to establish and contrast the independent and combined roles of physical and imagined exercises to prevent mobility disability.

